4.10 Extended follow-up for days 16-43

After the initial 15-day follow up after vaccination, there will be an extended surveillance period for safety assessment from day 16 after vaccination for a total of 42 days. This will be accomplished by a telephone call or email through the REDCap system to the parents of the subjects, depending on their preference and their availability, at day 29 and at day 44 to determine the status of asthma control. On Day 29, subjects will be queried about concomitant medications and medical services utilization. On day 44, subjects will be queried about concomitant medications and medical services utilization, as defined above. The cACT score and PROSE score will also be completed at day 44.

Adverse events (AEs) will be recorded on the memory aid and will include the need for new prescription or nonprescription medications for the control of asthma, an unscheduled healthcare provider visit or consultation within 42 days after vaccination, any other clinically significant event occurring at any point during the study period. Serious AEs (SAEs) will also be monitored through 42 days after vaccination and will include events that result in death, were life threatening, result in subject hospitalization or prolongation of existing hospitalization, result in persistent or significant disability or incapacity. Additionally, important medical events that may not have resulted in death, were not life threatening, or did not require hospitalization might be considered SAEs when, according to appropriate medical judgment, they jeopardize the patient or subject and require medical or surgical intervention to prevent one of the outcomes listed above.

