2 FEASIBILITY STUDY OBJECTIVES

2.1 Study Objectives

Primary Objective

To assess the feasibility of conducting a randomized prospective safety study of LAIV4 versus IIV4 during the 42 days after vaccination in children aged 5-11 years with persistent asthma of varied severity (cclIV4 will be used as a surrogate for LAIV4)

Secondary Objectives

1. To compare proportions of local and systemic reactogenicity events during the 14 days after cclIV4 versus IIV4 in children with asthma aged 5-11 years.
2. To describe the unsolicited and serious adverse events in children receiving cclIV4 and IIV during the 42 days.
3. To compare proportions of asthma exacerbations during the 14 days after cclIV4 versus IIV4 in children with asthma aged 5-11 years.
4. To compare proportions of asthma exacerbations during the 42 days after cclIV4 versus IIV4 in children with asthma aged 5-11 years.
5. To explore differences between the cclIV4 and IIV4 groups regarding clinical asthma symptoms after vaccination and changes in asthma control before and after vaccination in children with asthma of varied levels of severity.

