- Memory aid (daily symptom and peak flow diary on vaccination day, Day 1, and for the next 14 days, through Day 15, and on day 43) will be reviewed with the parent and the parent will demonstrate ability to take temperature and will be instructed in the collection of post-vaccination asthma clinical symptoms and symptom scores, adverse event, fever and concomitant medication administration data for 14 days (until day 15) after vaccination
- Parent/guardian will be given a thermometer and a ruler to use for daily temperature and local reactions recording, respectively
- Study staff will record any immediate adverse events (AEs) after vaccination occurring while still in the clinic
- Study staff will educate the family to notify the study staff if the patient requires an additional unscheduled medical visit for management of asthma symptoms (medical services utilization) or a new asthma control medication that has been prescribed.

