4.3.4 Visit 4 [Day 15 (- 1 through +2)] – Call/email

- Memory aid review for solicited symptoms
- Unsolicited symptoms review
- Concomitant medications review
- Post-vaccination asthma clinical symptoms review and symptom scores
 - Asthma control assessment (cACT)
 - PROSE
- Medical services utilization review
- Peak flow measurements
- Parent will be instructed to contact the study staff if the child utilizes medical services, has a new asthma medication prescribed, or experiences a serious adverse event

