2. The nature and frequency of the unsolicited and serious adverse events will be described in children receiving cclIV4 and IIV4 during the 42 days.
3. Proportions of asthma exacerbations in recipients of cclIV4 and IIV4 during the 14 days post-vaccination (until day 15). The asthma exacerbation proportion within 14 days post-vaccination will be calculated for children receiving cclIV4 or IIV4 influenza vaccine. For this calculation a child with an asthma exacerbation (as defined earlier in the protocol) on one or more days during day 1-15 would be considered to have had an asthma exacerbation (dichotomous yes or no). We will compare proportions in children receiving cclIV4 vs. IIV4.
4. Proportions of asthma exacerbations in recipients of cclIV4 and IIV4 during the 42 days post-vaccination (until day 43). The asthma exacerbation proportion within 42 days post-vaccination will be calculated for children receiving cclIV4 or IIV4 influenza vaccine. For this calculation a child with an asthma exacerbation (as defined earlier in the protocol) on one or more days during day 1-43 would be considered to have had an asthma exacerbation (dichotomous yes or no). We will compare proportions in children receiving cclIV4 vs. IIV4.
5. Proportions of clinical symptoms after vaccination and changes in measurement of asthma control, before and after vaccination in children with asthma of varied levels of severity, between recipients of cclIV4 or IIV4 will be assessed through five measures (see methods for schedule):
 - A. Proportions of subjects with asthma symptoms as assessed on memory aid (e.g., wheezing, nighttime awakenings, cough) during days 1 through 15.

Proportions of subjects with each asthma symptom (dichotomous yes or no) by treatment group, and asthma severity level will be calculated and a 95% confidence interval of the difference in proportions between the treatment groups will also be presented.
 - B. Change in Peak Expiratory Flow Rate (PEFR) after vaccination from baseline (pre-vaccination) PEFR.

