10.1 Data collection and management

The amount of data that will be collected for the proposed feasibility study will be limited in quantity, but a large, multisite study based on this feasibility study would be substantial and would require a sophisticated, practical and flexible system that can accommodate different modes of data collection and several separate linked surveys. The novel Vanderbilt-designed resource developed specifically for online collection of research information, the REDCap platform, will be used to design study forms, including the reaction forms, and short customized questionnaires to collect information from study subjects. This system will be used by Vanderbilt, Cincinnati and Duke for data management. All electronic linkages will fulfill regulations for protection of human subjects and requirements to minimize the risk of breach of confidentiality. After initial set-up, the work load required for electronic data collection will be substantially reduced (description of REDCap resources below).²² The Vanderbilt, Cincinnati and Duke investigators have previously used the REDCAP system for collection and analysis of large quantities of data. Participants' parents/guardians will be given the option to fill out their reactogenicity diary either directly in the REDCap system or on paper. Participants who choose the paper form will receive a phone call on day 3-6, 7-9, 14-17, 27-31, and 44-47 post-vaccination to collect the information recorded on their memory aid, which will then be entered by study personnel onto REDCap. All study-related documents containing protected health information, e.g. enrollment logs, case report forms, memory aids completed by study participants, will be maintained in secure research offices at Vanderbilt, Cincinnati and Duke, respectively, which are accessible to research staff only.

Vanderbilt Research Electronic Data Capture (REDCap)

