Education provided at first visit is understandable	Before leaving the clinic, all parents or guardians will demonstrate: 
 • proper use and care of the digital peak flow meter • proper use and care of oral digital thermometer • proper use of study ruler to assess erythema and induration • proper use of paper and/or electronic data entry forms
Memory Aid Data Completion through Day 15	At least 80% of the patients will complete the memory aid for 11 of the 15 day monitoring period
Memory Aid Data Completion Day 16 through day 43	At least 70% of the patients will complete the memory aids for Day 16 through 43
Peak Flow measurements (early study)	At least 75% of subjects will perform and document all home digital peak flow measurements (per protocol) for on at least 11 of the 15 day monitoring period.
Peak flow measurement (late study)	At least 70% of subjects will perform and document the digital peak flow for Day 42.
Nighttime awakenings (done in am)	At least 70% of subjects will document nighttime awakenings for at for on at least 11 of the 15-day monitoring period.
Day 4 (-1 to +2) call	At least 80% of study subjects will respond to Day 4 call and provide requested data (ACT and Prose are administered on the call)
Day 8 (± 2) call	At least 80% of study subjects will respond to Day 8 call and provide requested data. (ACT and Prose are administered on the call)
Day 15 (-1 to +2) call	At least 80% of study subjects will respond to Day 15 call and provide requested data. (ACT and Prose are administered on the call)
Day 29 (± 2) call	At least 70% of study subjects will respond to Day 29 call and provide requested data.
Day 44 (+3) call	At least 70% of study subjects will respond to Day 44 call and provide requested data. (ACT and Prose are administered on the call)
Parental Satisfaction survey	At least 70% of parents will complete the Parent/Guardian satisfaction survey

Schedule of Events

Table A2.

Study Visit	Enrollment Visit 1 (Vaccination)	Visit 2	Visit 3	Visit 4	Visit 5	Visit 6
Study Day	1	4	8	15	29	43
Visit Window (Days)	n/a	3-6	7-9	14-17	27-31	44-47
Type of Visit	Clinic	Call/email	Call/email/clinic ^a	Call/email	Call/email	Call/email
Obtain Informed Consent	X					
Obtain Assent (if applicable per site's IRB requirement)	X					
Review Eligibility Criteria	X					
Document Prior Year Flu Vaccination	X					
Review Medical History	X					
Review Asthma History	X					
Assess asthma clinical symptoms ^b (PROSE)	X	X	X	X		X

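### The plan contradicts itself on collecting unsolicited adverse events after Day 15, so the 42-day description may miss non-serious, unattended, untreated events on Days 16-43

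*Combined protocol and SAP*

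**What the plan says.** **The promise.** Section 2.1, secondary objective 2, reads "To describe the unsolicited and serious adverse events in children receiving" the two vaccines, over 42 days. Section 8, secondary outcome 2, repeats it with a frequency: "The nature and frequency of the unsolicited and serious adverse events will be described in children receiving" either vaccine, over the same 42 days.

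**Text that ends unsolicited-event collection at Day 15.**
- Section 4.3.1 trains parents to collect "adverse event, fever and concomitant medication administration data for 14 days (until day 15) after vaccination".
- Sections 4.3.2 to 4.3.4 (Visits 2-4) each list a review of unsolicited symptoms. Sections 4.3.5 and 4.3.6 (Visits 5-6) do not.
- Section 4.10, on the late contacts, says "On Day 29, subjects will be queried about concomitant medications and medical services utilization". The Day 44 contact repeats those two items and adds the cACT and PROSE scores.
- Table A2 marks the row for adverse-event collection and memory-aid review at Visits 1-4 only. The row for serious events and medical utilization runs to Visit 6.
- The last listed instruction to parents (section 4.3.4) is to contact staff "if the child utilizes medical services, has a new asthma medication prescribed, or experiences a serious adverse event".

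**Text that implies collection to Day 43.**
- Section 4.10 also places adverse events on the memory aid, including "any other clinically significant event occurring at any point during the study period".
- Section 10.1 schedules calls to families using paper forms, the last two on days "27-31, and 44-47 post-vaccination to collect the information recorded on their memory aid".
- Table A1 sets a benchmark: "At least 70% of the patients will complete the memory aids for Day 16 through 43".

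**The concern.** The two sets of text cannot both be followed. A site working from the visit lists and Table A2 would stop asking about unsolicited events after Day 15. A site working from the second paragraph of 4.10, section 10.1 and Table A1 would retrieve them from the memory aid. Capture could then be incomplete, and could differ between sites or between paper and REDCap families. A reported 42-day frequency would mix a period of active review with one of uncertain review and would be hard to interpret.

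The ambiguity also reaches the primary outcome. The Day 16-43 memory-aid benchmark is one of the quantitative feasibility measures, but section 4.3.1 describes a diary for Days 1-15 and Day 43 only. What counts as a completed aid for Days 16-43 is therefore not defined.

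**Working it through.** The plan states no figure to reproduce. The check sets the passages side by side and counts days.

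**1. Which late events have a scheduled query (Visits 5-6)?**

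| Type of event, Days 16-43 | Scheduled query | Source |
|---|---|---|
| Serious | Yes | Table A2, serious-event row |
| Medically attended | Yes | 4.3.5, 4.3.6, 4.10, Table A2 |
| Treated with medication | Yes | 4.3.5, 4.3.6, 4.10, Table A2 |
| Asthma symptoms and control | In part, at Visit 6 | cACT, PROSE and peak flow in 4.3.6 |
| Other non-serious, unattended, untreated | None; depends on a late memory aid | Sources conflict |

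**2. Could the gap in Table A2 come from text extraction?** Unlikely. Blank cells survive elsewhere in the table (peak flow is blank at Visit 5 and marked at Visit 6), and the adverse-event row agrees with the visit text in 4.3.5 and 4.3.6.

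**3. Length of the window.** With vaccination on Day 1, the post-vaccination window is Days 2-43, which is 42 days. Days 16-43 are 43 − 16 + 1 = 28 days. 28/42 = 66.7% (28/43 = 65% if Day 1 is counted).

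**4. Possible loss.** The documents give neither an unsolicited-event rate nor a late-capture rate, so both are assumed here. Let c be the fraction of late events of the last type in the table that are captured, and let the event rate be constant. Then:

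- share of events missed = (1 − c) × 28/42
- reported proportion of children = 1 − exp[−h(14 + 28c)], where h = −ln(1 − p)/42 and p is the true 42-day proportion

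For an assumed p = 0.30, h = 0.3567/42 = 0.00849 per day:

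| c | Share of events missed | Reported proportion (true 30%) |
|---|---|---|
| 1 | 0% | 30.0% |
| 0.75 | 16.7% | 25.7% |
| 0.50 | 33.3% | 21.2% |
| 0.25 | 50.0% | 16.3% |
| 0 | 66.7% | 11.2% |

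Between c = 1 and c = 0, an assumed true 20% would be reported as 20.0% down to 7.2%, and an assumed true 50% as 50.0% down to 20.6%.

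**The case against.** The best defence is that section 4.10 already covers these events. Its Day 29 sentence does not exclude other questions, and its next paragraph puts adverse events on the memory aid for the whole study. Sections 4.10 and 10.1 can be read as two routes to the same diary, one by direct REDCap entry and one by telephone. Section 4.9 also tells families to report exacerbation symptoms whenever they occur, and Visit 6 repeats the asthma measures. On this reading the residue is small: events that are clinically significant yet non-serious, unattended and untreated. The memory-aid and REDCap forms are not in the documents, so actual data loss and uneven capture between sites are not demonstrated.

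Part of this stands. Late collection is not wholly absent, the loss is possible rather than shown, and zero capture would require three passages to be disregarded. The rest does not remove the conflict. Section 4.9 and the Visit 6 measures address asthma symptoms, not other events. Section 4.10 lists what adverse events include; it does not limit outcome 2 to clinically significant ones. Naming the memory aid as the place to record does not help if parents are trained to stop at Day 15 and no visit list or Table A2 cell schedules a review of later entries.

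**Conclusion.** The concern holds. The plan promises a 42-day description of unsolicited events, and its own passages disagree on whether the non-serious, unattended, untreated ones are collected in the last 28 of those 42 days. The size cannot be determined from the documents. Under a constant event rate, between 0% and 67% of such events would be missed, depending on how many late ones are captured.

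The consequence is limited. The outcome is secondary and descriptive in a feasibility study of about 50 children, the schedule is the same in both arms so no between-arm bias is shown, and serious events, medical utilization and medications are still followed to the final contact. It should still be fixed: following the visit lists and Table A2 as written could undercount the stated frequency, and the study's purpose is to test procedures for a later safety trial.

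**What to change.** **Preferred.** Add a review of unsolicited symptoms to sections 4.3.5 and 4.3.6 and to the late-contact content in 4.10. Mark adverse-event collection at Visits 5 and 6 in Table A2. State in 4.3.1 what the memory aid collects on Days 16-43 and how often, so that parent training agrees with 4.10, 10.1 and the Table A1 benchmark.

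**Alternative.** Restate objective 2 and outcome 2 as unsolicited events through Day 15, with serious and medically attended events through Day 43. Then align the whole-study wording in 4.10, the late memory-aid calls in 10.1 and the Day 16-43 benchmark in Table A1.

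**Cost.** The preferred route needs one extra question at two contacts already scheduled, plus protocol wording and whatever matching change the memory-aid form and parent training require. The alternative needs wording changes only, but gives up the 42-day description for events that are neither serious nor medically attended.

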5 RISKS

5.1 Vaccines

All participants will receive the CDC VIS before vaccination. With any medicine, including vaccines, there is a chance of reactions. These are usually mild and go away on their own, but serious reactions are also possible. Any medication or vaccine can cause a severe allergic reaction, including anaphylaxis. Such reactions from a vaccine are very rare, estimated at about 1 in a million doses, and would happen within a few minutes to a few hours after the vaccination. As with any medicine, there is a very small chance of a vaccine causing a serious injury or death.

5.2 Inactivated Influenza Vaccine (IIV)

ACIP routinely recommends IIV for children with asthma⁷⁻⁹ and risks after IIV would be no higher than those encountered through usual care. Most people who get a flu shot do not have any problems with it. Minor problems following a flu shot include soreness, redness, or swelling where the shot was given, hoarseness, sore, red or itchy eyes, cough, fever, aches, headache, itching, fatigue. If these problems occur, they usually begin soon after the shot and last 1 or 2 days. More serious problems following a flu shot can include the following: There may be a small increased risk of Guillain-Barré Syndrome (GBS) after inactivated flu vaccine. This risk has been estimated at 1 or 2 additional cases per million people vaccinated, primarily in adults. This is much lower than the risk of severe complications from flu, which can be prevented by flu vaccine. Problems could happen after any injected vaccine: People sometimes faint after a medical procedure, including vaccination. Sitting or lying down for about 15 minutes can help prevent fainting, and injuries caused by a fall. Some people get severe pain in the shoulder and have difficulty moving the arm where a shot was given. This happens very rarely.

6 REPORTING OF ADVERSE EVENTS

SAE and AE reporting will occur consistent with routine practice. Vaccine-associated SAEs will be medically attended per standard procedures, and reported to the Vaccine Adverse Event Reporting System (VAERS) in accordance with standard procedures, and information about such events will be included in the study data (<https://VAERS.hhs.gov>). SAEs will be reported promptly to the overseeing IRBs in accordance with institutional procedures. Any unanticipated problems resulting from study conduct related to participation will be promptly reported to the reviewing IRBs including the CDC, in accordance with institutional procedures.

An SAE is an AE meeting one or more of the following criteria

- Life-threatening illness
- Death
- Hospitalization - An event requiring inpatient hospitalization
- Prolongation of existing hospitalization
- Persistent or significant disability/incapacity

Additionally, important medical events that may not have resulted in death, were not life threatening, or did not require hospitalization might be considered SAEs when, according to appropriate medical judgment, they

jeopardize the patient or subject and require medical or surgical intervention to prevent one of the outcomes listed above. These will be reported to the IRBs.

Participants who report severe solicited AEs or SAEs or express any concern about symptoms/unsolicited events will be encouraged to follow up with their pediatrician or primary care provider. Study staff will assist with coordination of referral appointments as necessary.

7 STUDY WITHDRAWAL/DISCONTINUATION

Subjects may voluntarily withdraw their consent for study participation at any time and for any reason, without penalty.

A subject may withdraw or be withdrawn from this study for any of the following reasons:

- Medical disease or condition, or any new clinical findings for which continued participation, in the opinion of the site principal investigator or appropriate sub-investigator, would compromise the safety of the subject, or would interfere with the subject's successful completion of this study, or would interfere with the evaluation of responses.
- As deemed necessary by the site principal investigator or appropriate sub-investigator for noncompliance or other reasons.
- Subject withdrawal of consent.
- Subject lost to follow-up.
- Termination of this study.
- New information becomes available that makes further participation unsafe.

Subjects may withdraw their consent for study participation at any time and for any reason, without penalty.

7.1 Handling of Withdrawals

Subjects who withdraw from the study before receiving vaccine will be replaced. Subjects who withdraw from the study after receiving vaccine will not be replaced. Every attempt should be made to collect all data specified by the protocol relative to study vaccine received up to the time of withdrawal. All SAE's and AE's that require VAERS reporting will be followed to adequate resolution or until considered stable.

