4 STUDY DESIGN AND PROCEDURES

This is a prospective randomized, open label clinical trial in approximately 50 children aged 5-11 years with a physician diagnosis of persistent asthma. The study will be conducted at three sites: Vanderbilt University Medical Center (Lead site), Cincinnati Children's Hospital Medical Center (contributing site), and Duke University Medical Center (contributing site). Subjects will be randomized 1:1 to receive either a single intramuscular dose of licensed Flucelvax[®] Quadrivalent (ccIIV4) or a single intramuscular dose of licensed Fluarix[®] Quadrivalent (IIV4), stratifying by asthma severity (mild vs. moderate/severe).

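### After an investigator withdraws a vaccinated child, Section 7.1 does not require anyone to look for new safety events, although Sections 4.10 and 8 call for them over 42 days

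*Combined protocol and SAP*

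**What the plan says.** Section 7 lists the reasons for which a child may leave. One rests on the investigator's judgment that staying in the study is unsafe for the child, or gets in the way of finishing it or of judging responses: "Medical disease or condition, or any new clinical findings for which continued participation, in the opinion of the site principal investigator or appropriate sub-investigator". Another is noncompliance or other reasons. Withdrawn consent is a separate item on the same list.

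Section 7.1 then applies one rule to all of them: "Every attempt should be made to collect all data specified by the protocol relative to study vaccine received up to the time of withdrawal". The next sentence adds: "All SAE's and AE's that require VAERS reporting will be followed to adequate resolution or until considered stable". Vaccinated children who leave are not replaced. Section 11.3 treats the two kinds of withdrawal alike as well: the family's agreement to complete evaluations lapses whether the child withdraws or is withdrawn.

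Other sections assume a full window. Section 4.10 states: "Serious AEs (SAEs) will also be monitored through 42 days after vaccination". In Section 8, outcome 2 covers unsolicited and serious events over 42 days, outcome 4 scores exacerbation as yes or no over Days 1 to 43, and outcome 5E covers medical utilization over 42 days. Table A2 places SAE and medical-utilization review at every visit through Visit 6.

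On design, Section 4 says: "This is a prospective randomized, open label clinical trial in approximately 50 children aged 5-11 years", and "Subjects will be randomized 1:1 to receive either a single intramuscular dose".

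**The concern.** In a trial with repeated dosing, withdrawing a sick participant stops exposure. Here the exposure is complete on Day 1. What remains is calls or emails, a diary and home peak flow. An investigator withdrawal after vaccination therefore stops no study treatment and mainly ends observation.

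A new clinical finding is one of the permitted grounds, so the loss can be related to the outcomes being measured. Allocation is open, so a discretionary decision could also differ by arm. Later events that nobody asks about cannot be restored at analysis. The study is meant to inform a future LAIV4 safety study, so the withdrawal rule could carry over to a trial where safety is the main question.

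**Working it through.** The documents give no withdrawal rate, exacerbation rate or power figure, so there is no stated figure to reproduce. The check is a reading of the text, followed by illustrative arithmetic.

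**1. What is still required after an investigator withdrawal**
- SAE or VAERS-reportable AE already known: followed to resolution or stability (Section 7.1).
- Exacerbation already recorded: the child is already a *yes*, so nothing is lost from that proportion.
- New SAE, new unsolicited AE, first exacerbation or medical visit: wanted through 42 days (Sections 4.10 and 8), but Section 7.1 does not require it to be sought.
- Classifying a child with an unfinished window in the yes/no outcomes: Section 8 gives no rule.

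**2. Reach of the follow-up exception.** The phrase about VAERS reporting may qualify AEs only, or both SAEs and AEs. Section 6 ties VAERS reporting to vaccine-associated SAEs. On the narrower reading, even a known SAE judged unrelated to vaccine falls outside the exception.

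**3. Window at stake.** Take a child withdrawn on Day 6 (day chosen for illustration). That is 6 − 1 = 5 days after vaccination, leaving 42 − 5 = 37 days and the Day 8, 15, 29 and 44 contacts.

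**4. Weight of one child.** 50 / 2 = 25 per arm, and 1/25 = 4 percentage points if a child with a missed first event stays in the denominator as *no*. If the child is dropped instead, the error is slightly smaller. With 5 true cases assumed, 5/25 = 20.0% becomes 4/24 = 16.7%, a gap of 3.3 points.

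**5. Range of the between-arm difference.** With equal recorded events and m children per arm whose status is unknown, the difference can lie anywhere within ±m/25 (m is an assumption):
- m = 1: ±4 points
- m = 2: ±8 points
- m = 3: ±12 points

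**6. Scale.** With complete data, the 95% Wald half-width is 1.96 × √(2p(1−p)/25). At an assumed risk of 10% this is 1.96 × √0.0072 = 16.6 points. At 20% it is 1.96 × √0.0128 = 22.2 points.

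**7. The benchmark does not guard against this.** Table A1 asks for at least 70% response at Day 44. 0.70 × 50 = 35, so the benchmark is met with 15 children lacking that contact.

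**The case against.** Section 7.1 sets a minimum effort. It does not forbid later contact, and Section 4.10 makes no exception for withdrawn children. Section 7 says a child may be withdrawn, not that illness triggers withdrawal. Elsewhere exacerbations are treated as outcomes to capture: families are told to report unscheduled visits, and records may be collected. With only calls, diaries and peak flow left, the safety ground would seldom be met. All this stands, and it limits how often the gap would matter. It does not close the gap, because a site following Section 7.1 as written has no duty to make the later contacts.

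A reader might infer several stronger things that the documents do not support:
- *That data collection ends at withdrawal.* The second sentence of Section 7.1 continues follow-up of known SAEs and VAERS-reportable AEs.
- *That a child withdrawn because of an exacerbation disappears from the exacerbation outcomes.* That child already counts as *yes*, and a repeat episode changes neither proportion.
- *That both arms will look safer.* This is not uniform. In outcome 5E, cutting follow-up short after a visit raises the rate. Pooled over an arm the effect is small: 25 × 42 = 1,050 days, and losing 37 of them moves one visit from 1/1,050 = 0.00095 to 1/1,013 = 0.00099 per day, under 4%.
- *That ill children will be withdrawn, or withdrawn differently by arm.* Both are possible under the wording; nothing shows that either is expected.
- *That no analysis can help.* The mixed model planned for PEFR uses partial records and can accommodate dropout that depends on recorded values. Only unseen later events are beyond recovery.

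**Conclusion.** The point holds in a limited form. Sections 7.1, 4.10 and 8 do not fit together for a vaccinated child withdrawn by the investigator: 42-day ascertainment is promised, but detection of new events after withdrawal is not required.

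The size is 4 percentage points of an arm's proportion per child whose later first event is missed. This assumes about 25 per arm, that the child is counted as *no*, and that such a child exists; the documents give no number. For a child withdrawn after a non-serious event, the 4 points apply to the SAE proportion only if a first SAE then follows within the window.

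The consequence is modest. The primary outcome is feasibility, SAEs are only described, no power is claimed, and the interval for a difference is already about ±17 to ±22 points at the assumed risks. The point is worth acting on because the correction is cheap and the loss may be related to outcome.

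**What to change.** Reconcile Section 7.1 with Sections 4.10 and 8. State that for a vaccinated child withdrawn for any reason other than withdrawal of consent to further contact, diaries and peak flow may stop, but the scheduled SAE, medication and medical-utilization contacts continue through Day 43/44. Medical visits and new systemic corticosteroid prescriptions are what make an episode count under the protocol's exacerbation definition, so these contacts would also supply most of what outcome 4 needs.

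Clarify whether the VAERS-reporting phrase in Section 7.1 limits SAEs as well as AEs.

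The grounds for withdrawal in Section 7 need not be deleted. It is enough to say that they end study procedures and not safety contacts. Section 11.3 should be made consistent. The consent form is not in the public copy, so whether it also needs a line cannot be checked here.

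The cost is a few sentences of amendment and a few more calls to families who have stopped other procedures. The contacts are already in the schedule.
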